### **B. PACT Experimental Arm**

1. Participants randomized to the PACT care arm will be electronically directed to the PACT website landing page which explains each step of the process. Participants will complete the initial PACT assessment for each lesson. Based on the assessment, the PACT website will provide personalized training lessons for each participant.
2. Participants will also participate in weekly phone coach sessions.
3. Participants will complete each lesson on a weekly basis in order to focus on, understand, and implement the steps in each lesson. New material will only be made available to participants every 7 days.
  - a. If participants fail to complete a lesson, they will be prohibited from accessing all future materials until the missed lesson is completed, even if it takes more than one week.
  - b. Participants who fail to complete each lesson within a month will be called by the study coordinator to identify if problem exists and may result in study withdrawal.
4. Participant will also continue participate in usual care from their dentist such as a splint or anti-inflammatory medications as needed. Some patients may be under care of another healthcare provider such as a physical therapist.
5. Adverse events will be recorded through the website assessments.

## **6.4 Final Study Visits (Final Visits, Weeks 8 and 16)**

All participants will be asked to complete the final follow-up outcomes evaluation at 8 weeks from the beginning of the intervention and at 16-weeks (2 months after program end). This includes questions about any adverse events and outcomes as reported by the participants during or after the lessons.

Participants will receive weekly email reminders from the web-system to complete the post-intervention questionnaires. There is a 2-week window in the completion of questionnaires at the 8-week and 16-week post-intervention time periods. If the questionnaire has not been completed at the 2-week period, participants will receive up to 3 reminder calls from the study coordinator to identify the barrier to completing the questionnaires and facilitate its completion.

If after two more weeks of time have passed without completion, the questionnaire will be not evaluable, and therefore, considered missing data.

At the end of the 8 week outcome questionnaire, participants will complete several program evaluation questions. In addition, at least ten randomly-selected subjects will complete a semi-structured qualitative interview about their experience in the program.

### **6.5 Withdrawal Visit**

If a participant is discontinued before study completion, prior to withdrawal of consent and with the participant's permission, an Early Termination visit will occur. Each of the procedures described for the Final Study Visit will be performed at (specify timeframe).

### **6.6 Unscheduled Visit**

Study participants are encouraged to work with the health coach on a regular basis, and may contact the Study Coordinator (SC) during the study. All contacts with the SC will be documented in the study records. PACT subjects will be able to make unscheduled calls to the health coach to have questions answered; however, they will be scheduled for future telehealth visits.

---

## 7 STUDY PROCEDURES/EVALUATIONS

### 7.1 Study Procedures/Evaluations

#### 7.1.1 Outcome Measure Questionnaires

The questionnaires that will be utilized are briefly described below. Copies of the questionnaires are reproduced in the appendix. All of the questionnaires are self-administered except for the qualitative interview which is conducted via phone by the study coordinator. For outcome measure questionnaires, responses will be recorded electronically through the study website.

Telephone Screen. This is a method used to screen for TMD pain. This questionnaire will be completed baseline and repeated at the final study visits.

Pain severity and Pain Interference. The Graded Chronic Pain Scale (GCPS) assesses 2 dimensions of pain: pain intensity and pain-related disability with mean intensity ratings for reported current, worst, and average pain.

Jaw Functioning. Jaw Functional Limitation Scale (JFLS-8) identifies daily activities interfered with by jaw pain. This 20-item instrument measures limitations across 3 domains: mastication (6 items), vertical jaw mobility (4 items), and verbal and emotional expression (8 items). Two items are not scored as part of these 3 subscales. A degree of limitation is rated on a 0-10 scale from 0 ("no limitation") to 10 ("severe limitation").

#### Hypothesized mediators

Self-efficacy. The Chronic Pain Self-efficacy Scale is a 22-item instrument that measures a person's beliefs in their capabilities to produce a given outcome, particularly regarding compliance and adherence with self-care in reducing pain. For the pilot study, we will be using the 5-item Self-efficacy for Pain management (PSE) subscale of the Chronic Pain Self-efficacy Scale.

Participant activation. The Patient Activation Measure (PAM) is a 7-item instrument that gauges the knowledge, skills, and confidence essential to managing one's own health and health care. PAM segments consumers into 1 of 4 progressively higher activation levels, including disengaged, becoming aware, taking action, and maintaining behaviors.

Exercise frequency. Type and frequency of conditioning exercises are measured using two questions from the Global Physical Activity Questionnaire. The questions measure exercise habits.

Sleep quality. Quality of sleep is measured using four questions from the World Health Survey (WHO).

Catastrophizing. The Pain Catastrophizing Scale is a 14-item instrument that will be measured at baseline. Participants who cope poorly due to catastrophizing often have

negative outcomes.

Depression. The Patient Health Questionnaire (PHQ9) is a widely-used 9-item depression screen with questions covering the core DSM V screening criteria for diagnosing depression.  
74

Oral habits. The DC/TMD Oral Parafunctional Habits Scale measures frequency and duration of oral parafunctional habits that place repetitive strain on the jaw. 40

Perceived Stress Scale (PSS). This questionnaire assesses 10 sources of stress and produces an overall perceived stress rating and has been used to measure stress associated with chronic disease.

Social support. The Social Support Questionnaire (shortened version) is a 6-item questionnaire designed to measure perceptions of social support and satisfaction with that social support. 72

## **7.1.2 Program Evaluation and Qualitative Interview**

### **7.1.2.1 Program Evaluation**

As part of the 8-week follow up survey, the program evaluation involves 7 close-ended questions to assess participant experience with the overall program and an additional 11 close ended questions for participants involved in the PACT program to assess satisfaction and perceptions of the program.

### **7.1.2.2 Qualitative Interview of Participants**

At least 10 randomly selected participants will be asked to complete the qualitative interview. The qualitative interview involves 9 open-ended questions to assess participants' satisfaction and perceptions of the program.

### **7.1.2.3 Website issues**

Phone calls and questions received about web-site issues will be documented throughout the study to assess functionality of the website.

## 8 ASSESSMENT OF SAFETY

We will implement a meaningful safety system for the study by considering the risks of the study intervention, study procedures as well as the characteristics of the study population (individuals with TMD pain). There are no risks to other individuals in the study such as health coaches.

Specifications of Safety Parameters that will be recorded by the Study Coordinator for each participant in their research record include;

- The study coordinator will be in frequent contact with the health coaches to identify any potential participant concerns with study staff.
- The participants also have the phone number for the study coordinator to call if a concern related to the study program arises.

### 8.1 Specification of Safety Parameters

#### 8.1.1 *Unanticipated Problems*

It is believed that risks to participants in the present study are minimal. Both traditional and PACT self-care is currently used by many TMD clinicians in the U.S. and abroad. It has been used with a wide variety of people, including adults with TMD and has been used in previous research with no reported risks to the research participants. The Office for Human Research Protections (OHRP) considers unanticipated problems involving risks to participants or others to include, in general, any incident, experience, or outcome that meets **all** of the following criteria:

- Unexpected in terms of nature, severity, or frequency given (a) the research procedures that are described in the protocol-related documents, such as the IRB-approved research protocol and informed consent document; and (b) the characteristics of the participant population being studied;
- Related or possibly related to participation in the research (“possibly related” means there is a reasonable possibility that the incident, experience, or outcome may have been caused by the procedures involved in the research); and
- The research places participants or others at a greater risk of harm (including physical, psychological, economic, or social harm) than was previously known or recognized.

#### 8.1.2 *Adverse Events*

An **adverse event (AE)** is generally defined as any unfavorable and unintended diagnosis, symptom, sign (including an abnormal laboratory finding), syndrome or disease which either occurs during the study, having been absent at baseline, or if present at baseline, appears to worsen. Adverse events are to be recorded regardless of their relationship to the study intervention.

#### 8.1.3 *Serious Adverse Events*

A **serious adverse event (SAE)** is generally defined as any untoward medical occurrence that results in death, is life threatening, requires inpatient hospitalization or prolongation of existing hospitalization, results in persistent or significant disability/incapacity, or is a congenital anomaly.

The study intervention is a patient-centered self-management program for TMD pain. Potential participants with serious medical or psychiatric conditions are excluded from the study at initial screening. If study participants develop an increase in pain or other health concerns during the course of the study whether or not related to the study intervention would be considered an adverse event. The PACT program is a web-based, tailored 8-week program supported by a health coach to help enhance understanding, compliance, and success in self-management for TMD pain. There are self-report assessments at the end of each week throughout the entire program to monitor progress, compliance, adverse events, risk factors, and protective factors. If study subjects develop an aggravation of the pain or a new symptom that the subject attributes to the study intervention this would be considered an adverse event. This will be monitored by both self-report within the PACT program weekly assessments as well as by the dental professional who is caring for the patient. Adverse events will be reported to the Study Coordinator, the PI and the PO.

If participants screen for depression, we will provide a list of mental health providers who they can consult with to ensure their safety.

## **8.2 Events Qualifying as an Adverse Event or Serious Adverse Event for the Purpose of this Protocol**

Only those events considered to be related to the study intervention will be reported. A clinically significant change from the baseline in a pre-existing condition documented as screening will be reported as an AE if the change is considered at least possibly related to study intervention.

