## **8.3 Characteristics of an Adverse Event**

### **8.3.1 Relationship to Study Intervention**

All adverse events will have their relationship to study intervention assessed and documented in the participant research record and will be included in summary reporting to the IRB and the PI. Evaluation of relatedness will consider etiologies such as natural history of the underlying disease, concurrent illness, concomitant therapy, study-related procedures, accidents, and other external factors. In a clinical trial, the study intervention must always be suspect. AEs will be categorized according to the likelihood that they are related to the study intervention. Specifically, they will be labeled for this study as:

1. (Definitely unrelated, definitely related, probably related or possibly related to the study intervention)
  - a. The event is known to occur with the study intervention.
  - b. There is a temporal relationship between the intervention and event onset.
  - c. The event abates when the intervention is discontinued.
  - d. The event reappears upon a re-challenge with the intervention.
2. Not Related (Unlikely, Not Related)
  - a. There is no temporal relationship between the intervention and event onset.
  - b. An alternate etiology has been established.

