## **8.5 Reporting Procedures**

### **8.5.1 Adverse Events**

Study intervention-related AEs will be monitored throughout this study and recorded on a case report form at each visit. These events will be reported and reviewed by the PI as they occur, and reported to the IRB. DSM forms will be completed on a quarterly time frame for reporting and include summary reports of adverse events and others relevant to summary data will be reported to the DSM.

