### **8.5.3 Serious Adverse Event Reporting to NIDCR**

SAEs that are unanticipated, serious, and possibly related to the study intervention will be reported to the IRB, and NIDCR in accordance with requirements. Unexpected fatal or life-threatening AEs related to the intervention will be reported to the NIDCR Program Officer within 7 days. Other serious and unexpected AEs related to the intervention will be reported to the NIDCR Program Official within 15 days. Anticipated or unrelated SAEs will be handled in a less urgent manner but will be reported to the IRB, and NIDCR in accordance with their requirements. In the annual AE summary, the PI will state that they have reviewed all AE reports.

SAE Reporting Contact Information:

- Product Safety Fax Line (US): [name]
- Product Safety Fax Line (International): [contact]

- Product Safety Email: [rho\\[contact]](mailto:[contact])

General questions about SAE reporting can be directed to the Rho Product Safety Help Line (available 8:00AM – 5:00PM Eastern Time):

- US: [name]
- International: [contact]

The study clinician will complete a Serious Adverse Event Form and submit via fax or email within the following timelines:

- All deaths and immediately life-threatening events, whether related or unrelated, will be recorded on the Serious Adverse Event Form and submitted to Product Safety within 24 hours of site awareness.
- Serious adverse events other than death and immediately life-threatening events, regardless of relationship, will be reported by fax within 72 hours of site awareness.

All SAEs will be followed until resolution or stabilization.

The study coordinator will be responsible for compiling the data and producing the necessary reports, as well as assuring that all parties obtain copies of these reports. Adverse events will be reported and reviewed by [name] as they occur and reported to the IRB. The number of days by which a serious adverse event or unanticipated problem would be reported is 2 days. Summary reports of adverse events and others relevant to summary data will be reported to the PO at NIDCR. Reports will include description of study progress, subject recruitment, subject demographic data, subject status, and inclusion/exclusion criteria. These reports will be reviewed by the Principal Investigator and study team prior to presenting to NIDCR.

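### Sections 8.2, 8.4 and 8.5.1 keep only events judged related, other safety sections call for events whatever their relationship, and nothing says which rule prevails

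*Protocol*

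**What the plan says.** Three Protocol sections keep only related events.

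- Section 8.2: "Only those events considered to be related to the study intervention will be reported". Its second sentence makes a worsened pre-existing condition reportable as an AE only if the change is at least possibly related.
- Section 8.4: the investigator reports related SAEs and related unexpected AEs.
- Section 8.5.1: "Study intervention-related AEs will be monitored throughout this study and recorded on a case report form at each visit".

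The following places set no such condition.

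- Section 8.1.2, repeated in Appendix J II.A: "Adverse events are to be recorded regardless of their relationship to the study intervention".
- Section 8.1.3 says that increased pain or another health concern arising during the study, "whether or not related to the study intervention would be considered an adverse event". It adds: "Adverse events will be reported to the Study Coordinator, the PI and the PO".
- Section 8.3.1: every AE has its relatedness documented in the research record and goes into summary reports to the IRB and the PI.
- Appendix J Table 4: the AE listing has a code for definitely unrelated events.
- Section 8.5.3, for SAEs: "All deaths and immediately life-threatening events, whether related or unrelated, will be recorded on the Serious Adverse Event Form", and "Serious adverse events other than death and immediately life-threatening events, regardless of relationship, will be reported by fax within 72 hours of site awareness". It also sends unrelated SAEs to the IRB and NIDCR, less urgently.

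The first relatedness group in 8.3.1 reads "Definitely unrelated, definitely related, probably related or possibly related to the study intervention".

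**The concern.** A site cannot follow both sets of rules. Under 8.2 as written, an SAE judged unrelated is not reported, yet 8.5.3 requires its submission.

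The related-only set also turns relatedness from a description of an event into a condition for keeping it. Section 5.4.2 says that participants and researchers are not blinded, and no masked or independent assessor of AE relatedness is named. Jaw pain is both the condition under study and the most foreseeable AE, so attributing a flare to the programme or to the disease is a matter of judgement.

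Two uses depend on which events are kept. The Annual Report (section 11.3; Appendix J III.F) asks whether AE rates match pre-study assumptions. The first stopping criterion (section 5.6; Appendix J III.D) rests on adverse effects associated with the intervention. The pilot also tests methods for a multi-site trial, so an unresolved rule may be carried forward.

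**Working it through.** The plan gives no figure here, so the check sets the texts side by side and follows an event through them.

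| Pair | Same activity? | Can both hold? |
|---|---|---|
| 8.1.2 and 8.2 | No: recording against reporting | Yes: record all, report related |
| 8.2 and 8.5.3 | Yes: reporting SAEs | No |
| 8.2 and 8.1.3 | Yes: reporting AEs | No |
| 8.2 and 8.3.1 | Yes: reporting AEs, in summary form | No |
| 8.4 and 8.5.3 | Yes: reporting SAEs | Not if 8.4 sets the full scope |
| 8.5.1 and 8.1.2 | Yes: recording AEs | Only if the research record holds all events and the case report form a subset |

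**A hospitalisation judged unrelated.** Section 8.2 excludes it, and 8.4 does not ask for it. Section 8.5.3 requires a fax within 72 hours whatever the relationship.

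**Worsened jaw pain judged unrelated.** It is an AE under 8.1.2, which includes worsening of something present at baseline, and under 8.1.3. By 8.3.1 it enters the research record and the summary reports, and Table 4 has a code for it. By 8.2 it is not reported, and by 8.5.1 it is not on the case report form. Section 8.1.3 also names symptoms that the subject attributes to the intervention as AEs, but that sentence excludes nothing else.

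**An event labelled definitely unrelated.** In 8.3.1 this label is in group 1, above the criteria of known occurrence, timing, abatement on withdrawal and return on re-challenge. Those are criteria for relatedness. Group 2 holds the unlikely and not-related labels. Read literally, a definitely unrelated event falls in the related group. Appendix J II.C and Table 4 use one four-level scale without this problem.

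**Does anything resolve the conflict?** No text ranks the sections. The safety board in 8.6 receives only SAEs already described as related, so an event judged unrelated does not reach it. Appendix J III.E makes the PI the safety monitor. The SAP contains no adverse-event analysis that would fix which set is tabulated.

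**The case against.** The strongest reply is that unrelated events are already captured. Section 8.1.2 records them, 8.3.1 places them in the research record and summary reports, and Table 4 has a code for them. Section 6.3 records AEs through website assessments in both arms. On this view 8.5.1 only says which events are copied to the case report form. The study is also a minimal-risk descriptive pilot.

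Much of this stands. The 8.5.1 and 8.1.2 wording is a tension, and a two-record reading is possible though untidy. The documents do not show that the related-only rules govern. But the reply does not touch 8.2 against 8.5.3 on SAEs, or 8.2 against 8.1.3 and 8.3.1 on AE reporting.

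A reader might infer more than the documents support:

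- **That a planned comparison of AEs between arms is biased.** None is planned. Section 11.4 and the SAP contain no AE analysis, the AE and SAE tables in Appendix J have no arm column, and Appendix J I.C keeps group-identifiable material out of AE reports and annual summaries.
- **That control-arm events will seldom be called related, by some stated amount.** The documents give no attribution rate for either arm, and the control arm also receives active self-care advice. Any figure would follow from the rates chosen.
- **That 8.5.3 requires all events.** Its rule covers SAEs only.
- **That relatedness simply decides what is counted.** This holds only if 8.2, 8.4 and 8.5.1 prevail.

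**Conclusion.** The point holds as an internal contradiction with a conditional consequence. Three sections (8.2, 8.4, 8.5.1) restrict reporting or AE case-report-form entry to related events. Four places (8.1.2, 8.1.3, 8.3.1, Appendix J Table 4) call for AEs regardless of relationship, and 8.5.3 does so for SAEs. The clearest failure is that 8.2, followed literally, drops unrelated SAEs that 8.5.3 requires. Section 8.3.1 adds a misplaced category.

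If the related-only rules govern, a relatedness judgement in an unblinded study filters the case report form and the safety reports, and so the AE rates and the safety stopping criterion. That the person judging knows the arm is inferred from 5.4.2, because no AE assessor is named. The contradiction itself needs no assumption about rates, and no numerical size can be given. It should be corrected before use, in proportion to a minimal-risk pilot.

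**What to change.** - **Sections 8.2, 8.4 and 8.5.1:** state that all AEs and SAEs are recorded on the case report form and included in the AE listing and summary reports, regardless of relationship. Relatedness is a recorded descriptor and not a condition for entry. Section 8.4 must be included, or the conflict survives there. The second sentence of 8.2, on pre-existing conditions, needs the same change.
- **Section 8.3.1:** replace both groups with the single scale of Appendix J II.C and Table 4 (definitely unrelated, possibly, probably, definitely related). Moving one label would leave the unlikely and not-related labels beside that scale.
- **SAE scope:** state that all SAEs are in reporting scope, as in 8.5.3. That section holds several clocks (24 hours, 72 hours, 2 days, 7 days, 15 days), which must be reconciled separately. Pointing to 8.5.3 does not settle them.
- **By-arm summary, if wanted:** place it in the final descriptive report, so that interim AE reports and annual summaries still meet Appendix J I.C.

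The cost is a protocol wording amendment, which needs IRB approval under section 14.2, and a few more rows in the AE listing.
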